CFR – Code of Federal Regulations

CPT – Consumer Product Testing Company, Inc.

CRF – Case Report Forms

GCP – Good Clinical Practice

HIPAA - Health Insurance Portability and Accountability Act

ICF – Informed Consent Form

IRB – Institutional Review Board

PI – Principal Investigator or designee

SAE – Serious Adverse Event

SOP – Standard Operating Procedure

DEFINITIONS

Adverse Event (AE): Any negative experience that a participant has during the course of a clinical trial, including new or worsening symptoms or laboratory abnormalities.

Belmont Report: A document entitled "Ethical Principles and Guidelines for the Protection of Human Subjects of Research" that was produced by the National Commission for the Protection of Human Subjects of Biomedical and Behavioral Research in 1978. The Belmont Report identifies three fundamental ethical principles for all human subjects' research: respect for persons, beneficence, and justice.

Blinding: When research participants are unaware of the assigned "treatment." In a single-blinded trial, the subjects do not know what treatment they are receiving. In a double-blinded trial, the subjects AND the investigators are unaware of the treatment assigned, as are the monitors and statisticians in some cases.

Case Report Form (CRF): A record of information collected on each subject during the clinical trial.

Clinical Investigation: A systematic trial designed to evaluate a test material in humans.

Clinical Research: A trial in human subjects.

Clinical Trial: Any prospective investigation in which the applicant or investigator determines the method of assigning the test material or other interventions to one or more human subjects.

Declaration of Helsinki: A series of guidelines adopted by the 18th World Medical Assembly in Helsinki, Finland in 1964. Recommendations include the procedures required to ensure subject safety in clinical trials, including informed consent and Ethics Committee reviews.

Ethics Committee: An independent group of medical and nonmedical people who verify the integrity of a trial and ensure the safety, integrity, and human rights of the subjects.

Exclusion Criteria: Characteristics that would prevent a subject from being eligible to participate in a research trial, as specified in the protocol.

Good Clinical Practices (GCPs): International ethical and scientific quality standards for the design, conduct, monitoring, recording, auditing, analysis, and reporting of trials.

Health Insurance Portability and Accountability Act (HIPAA): Legislation passed in 1996 that includes a privacy rule creating national standards to protect personal health information.

Inclusion Criteria: A list of requirements that a subject must meet to be eligible to participate in a research trial, as specified in the protocol.

Informed Consent: The verification of a person's willingness to volunteer in a research trial. The verification is requested only after the person has received complete, objective information about the research, including its objectives, potential benefits, risks and inconveniences, alternative therapies that may be available (if applicable), and the subject's rights and responsibilities in accordance with the current revision of the Declaration of Helsinki (as amended). Consent is given by executing the Informed Consent Form (ICF).

Institutional Review Board (IRB): An independent group of professionals designated to review and approve the clinical protocol, Informed Consent Forms, trial advertisements, and patient brochures to ensure that the trial is safe and effective for human participation. The IRB also ensures that the trial adheres to FDA regulations.

Investigator: A medical professional, usually a physician but also sometimes a nurse, pharmacist, or other professional, under whose direction a test material is given or dispensed. A principal investigator (PI) is responsible for the overall conduct of the clinical trial.

NNAU01-001 20180213 RIPT

Protocol: NNAU01-001 Revision Date: 2/13/18

Page: 5 of 21

MedWatch Program: A national educational/promotional initiative to educate health professionals about the importance of reporting serious adverse events and important product problems, to facilitate reporting to the FDA if they choose to do so, and to provide feedback to the health professional community as new safety information becomes available.

Monitor: The Sponsor or CRO representative who reviews trial records to determine that it is being conducted according to the protocol.

Monitoring: Reviewing a clinical trial, ensuring that conduct, proper records, and reports are in accordance with the approved protocol, standard operating procedures, GCPs, and regulatory requirements.

Protocol: A detailed plan that sets forth the objectives, design, and methods for a clinical trial.

Protocol Amendment: Changes or clarifications made in writing to the original protocol.

Quality Assurance: Systems and procedures designed to ensure that a trial is being performed in compliance with the approved protocol, standard operating procedures, GCPs, and that the data being generated are accurate.

Randomization: A method of assigning trial test material such that each subject has an equal chance of being assigned to each treatment or control group. Randomization guards against selection bias.

Serious Adverse Event (SAE): Any adverse event (AE) that is fatal, life-threatening, or permanently disabling, or that results in new or prolonged hospitalization, in a congenital anomaly/birth defect, or is an important medical event.

Source Data: All information contained in original records and certified copies of results or observations.

Source Documents: Where medical information is originally recorded, including physician notes, laboratory reports, discharge summaries, autopsy reports, etc.

Sponsor: The entity who takes responsibility for initiation, management, and financing of research.

Standard Operating Procedures (SOPs): Official, detailed, written instructions for the management of clinical trials. SOPs ensure that all the functions and activities of a clinical trial are carried out consistently and efficiently.

Subject: A patient or healthy person participating in a research trial.

Test Materials: Any material or product that is the subject of testing or a clinical trial. This may also be referred to as a "test article" or "investigational material."

6 of 21

14

SYNOPSIS

Name of Company: NeXtGen Biologics, Inc. Name of Investigational Test Materials:

NeoMatriX™ Lot: AD17H150932/AD17H150933

Title of Clinical Trial: A Human Repeated Insult Patch Test

Investigator: [name], CCRA, CCRC

Sub-Investigators: [name]; [name]

Clinical Trial Center: Consumer Product Testing Company, Inc., [name]

Publication (reference): None

Clinical Trial Period: Approximately 6 weeks; start

date to be determined

Phase of Development: I

Clinical Trial Design: This is a single-center repeated insult patch test in healthy male and female subjects aged 18 to 79 years, inclusive.

Objectives: The first primary objective of this trial is to determine by repetitive epidermal contact, the primary or cumulative irritation potential of a test material. The second primary objective of this trial is to determine by repetitive epidermal contact, the allergic contact sensitization potential of a test material.

Methodology: Subjects will be patched with a test material, a positive control and a negative control 10 times over 40 days, 9 during Induction Phase and 1 during Challenge Phase. Each patch will be worn for approximately two days. Before each patch application, the test site will be evaluated using the Erythemal Scoring Scale (ESS) and Additional Reaction Scoring. Following a Rest Phase of approximately 10 to 14 days, the subjects will again be patched on a virgin test site with the test material (but not the negative control nor the positive control). After two days of skin contact, the test sites will be evaluated using the ESS and Additional Reaction Scoring on removal day and Days 1 and 2 post-removal. The ESS and Additional Reaction Scoring results will be evaluated to determine the allergic potential of the test material. The three test sites will be as follows: test material; saline negative control; and positive control (0.4% SLS).

Number of Subjects Planned and Analyzed: Approximately 57 subjects will be enrolled in the trial so that at least 50 subjects will complete the trial. Data from all subjects who complete the Induction Phase will be analyzed for irritant contact dermatitis potential. Data from all subjects who complete the Challenge Phase will! be analyzed for allergic contact sensitization potential.

[figure not shown]
Diagnosis and Main Criteria for Inclusion: Healthy adult male and non-pregnant females aged 18-79 years, inclusive.

Test Material, Dose and Mode of Administration, Batch Number: The test material, approximate 8 mm disc of NeoMatriX™, will be applied to the cotton pad of each patch. Patches consisting of the test material and controls will be applied to specific test sites on the back of each subject.

Duration of Treatment: Fresh patches of test material and controls during the Induction Phase (approximately 3 weeks); no patches during the Rest Phase (approximately 2 weeks); and one patch of test material during Challenge Phase (approximately 1 week). No negative control nor positive control will be applied during the Challenge Phase.

Criteria for Evaluation: Irritant contact dermatitis potential and allergic contact sensitization potential will be assessed through the evaluation of the test sites of application using the ESS and Additional Reaction Scoring. Statistical Methods: The ESS scores and Additional Reaction Scoring scores will be tabulated. The incidence of AEs, new-onset AEs, will be summarized. Maximum intensity and duration of AEs will be summarized by treatment group.

FLOW CHART OF TRIAL DESIGN

1 Background

A repeated insult patch test is a test devised to ascertain if an agent has the potential to cause contact irritation or contact allergy in the skin (Reference 12.1 and 12.2). Allergy is only elicited in immunologically competent individuals who have become sensitized through exposure to the agent following repeated cutaneous patch applications.

2 Trial Objective

The first primary objective of this trial is to determine by repetitive epidermal contact, the primary or cumulative irritation potential of a test material.

The second primary objective of this trial is to determine by repetitive epidermal contact, the allergic contact sensitization potential of a test material.

3 Proposed Schedule

Proposed trial initiation and termination dates will be established prior to the start of testing. The summary schedule of Induction Phase visits is shown in the table below.

[figure not shown]
Induction Phase Visits

The summary schedule of Rest Phase and Challenge Phase visits is shown in the table below.

K

, 3

Rest Phase and Challenge Phase Visits

4 Test Materials

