5.4 Withdrawal of Subjects

The subject is free to withdraw their consent to participate in the trial at any time and for any reason, in accordance with the principles of the World Medical Association Declaration of Helsinki (as amended) and of the Belmont Report. The PI also has the right to withdraw a subject from the trial for safety, lack of efficacy or administrative reasons.

Possible reasons why a subject may be withdrawn from the trial include the following:

- 1. Experiences a serious or intolerable AE;
- 2. Develops, during the course of the trial, symptoms or conditions listed in the exclusion criteria, including pregnancy;
- 3. Takes medications that are contraindicated, as described in the exclusion criteria;
- 4. Incurs a protocol violation such as failure to comply with the specified treatment regimen or failure to comply with the visit schedule; or
- 5. Requests an early discontinuation due to:
 - A clinical reaction for which the PI did not consider removal from the trial to be necessary;
 - Other (non-specific) subject-initiated reason

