5.5 Disposition of Withdrawn Subjects

The date the subject is withdrawn from the trial and the reason for discontinuation will be recorded on the CRF. All evaluations scheduled for the final trial visit will be completed as soon as possible after the subject is withdrawn from the trial.

When a subject fails to return for scheduled trial visits, the PI or designee will make a reasonable effort to contact the subject and determine why the subject failed to return. This information will be recorded on the CRFs. The PI will encourage all subjects who decide to withdraw from the trial to complete all evaluations, which may be necessary to assure that the subject is free of untoward effects, and to seek appropriate follow-up for any continuing problem.

Methodology

Page: 12 of 21

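### The irritation analysis is stated for Induction completers, so irritation is understated if subjects reacting at the test-material site leave Induction more often than others

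*Combined protocol and SAP*

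**What the plan says.** The synopsis (Number of Subjects Planned and Analyzed) gives the only irritation analysis set named in the visible text: "Data from all subjects who complete the Induction Phase will be analyzed for irritant contact dermatitis potential". It also plans for losses: "Approximately 57 subjects will be enrolled in the trial so that at least 50 subjects will complete the trial".

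The Statistical Methods entry of the synopsis says "The ESS scores and Additional Reaction Scoring scores will be tabulated" and names no set. Section 6.1 likewise says that the Induction scores will be analysed for irritation, without saying in whom. Section 7 plans no statistical methods, so it neither confirms nor widens the synopsis.

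Section 5.4 (Withdrawal of Subjects) lists possible reasons for leaving. One is "Experiences a serious or intolerable AE". Another, under early discontinuation at the subject's request, is "A clinical reaction for which the PI did not consider removal from the trial to be necessary". For subjects who leave, Section 5.5 provides that "the reason for discontinuation will be recorded on the CRF", and that "All evaluations scheduled for the final trial visit will be completed as soon as possible after the subject is withdrawn from the trial".

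**The concern.** Irritation at the test-material site is the outcome, and it is also a plausible reason for leaving. If leaving removes a subject from the irritation set, the set is selected on the outcome. The completer table then shows too little irritation whenever subjects reacting at the test-material site leave Induction more often than the rest.

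The first primary objective rests on this table. With about 50 to 57 subjects, one to three reactors can decide whether it shows no reactors or some. Anyone wanting to find the missing subjects would have to look for them in the AE summary.

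**Working it through.** **Inputs from the documents.** About 57 enrolled and at least 50 completing (synopsis); nine patchings in 21 days, with sites scored before each application (Section 6.1); site scores of 2 to 4 counted as AEs (Sections 6.4.1 and 6.4.2). The documents give no reaction rate, no dropout rate by phase and no expected reasons for leaving.

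**The plan's own figure.** The gap is 57 − 50 = 7, or 7/57 = 12.3%. No dropout rate is stated, so 57 cannot be derived independently. Assumed losses of 10%, 12% and 15% give 50/0.90 = 55.6, 50/0.88 = 56.8 and 50/0.85 = 58.8, rounded up to 56, 57 and 59. The figure is unremarkable.

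**Illustration by counts.** Assume that 57 subjects are patched and have a later reading, that k of them leave Induction for a test-material-site reaction, and that nobody leaves Induction for another reason. Let c be the number of completers who react. The stated set gives c/(57 − k); all patched subjects give (c + k)/57. Intervals are exact (Clopper-Pearson) 95%. When the count is zero the upper limit is 1 − 0.025^(1/n), for example 1 − 0.025^(1/54) = 6.6%.

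| k | c | Completers only | All patched with a later reading |
|---|---|---|---|
| 0 | 0 | 0/57 = 0% (0 to 6.3%) | 0/57 = 0% (0 to 6.3%) |
| 1 | 0 | 0/56 = 0% (0 to 6.4%) | 1/57 = 1.8% (0.04 to 9.4%) |
| 3 | 0 | 0/54 = 0% (0 to 6.6%) | 3/57 = 5.3% (1.1 to 14.6%) |
| 3 | 2 | 2/54 = 3.7% (0.5 to 12.7%) | 5/57 = 8.8% (2.9 to 19.3%) |
| 7 | 0 | 0/50 = 0% (0 to 7.1%) | 7/57 = 12.3% (5.1 to 23.7%) |

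The last row assigns the whole-trial gap to reaction-related exits in Induction. It is an upper bound, not an expectation.

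**Illustration by rates.** Assume that a fraction d = 7/57 leaves during Induction, that the true reactor rate is p, and that reactors leave RR times as often as others. Dropout is then d0 = d/(1 − p + p·RR) in non-reactors and d1 = RR·d0 in reactors, and the completer rate is p(1 − d1)/(1 − d). For p = 10% and RR = 2: d0 = 0.1228/1.1 = 0.112, d1 = 0.223, and 0.10 × 0.777/0.877 = 8.9%. In the same way:

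- p = 10%: 10.0%, 8.9%, 7.9% and 6.4% at RR = 1, 2, 3 and 5.
- p = 5%: 5.0%, 4.4%, 3.8% and 2.8%.
- p = 20%: 20.0%, 18.1%, 16.8% and 15.0%.

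The bias is downward when RR exceeds 1 and zero when RR equals 1. It reverses if reactors stay and others leave: with five reactors, none among seven leavers, completers show 5/50 = 10.0% against 5/57 = 8.8%. Exits caused by the positive control or by unrelated matters do not bias the test-material result unless they go together with test-material-site reactions.

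**The case against.** The strongest reply is that the exclusion may never occur. The visible text does not define completing Induction, and most of Section 6.3 is missing from this copy, so a rule on strong reactions or missed patches may stand there. Section 8.4 allows application of the test material to be interrupted or stopped, which is a different step from withdrawing the subject. A reactor whose patching stops could stay in the trial and count as a completer. The reasons in Section 5.4 are only possible ones, tied neither to Induction nor to the test-material site. The synopsis says that completers will be analysed; it does not say that only they will be. All of this stands. It limits the point to what follows from the synopsis as written, and the gaps in this copy are not a fault of the plan.

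A second reply is that the reactions are recorded elsewhere. A reader might infer that they would vanish from the report. The documents do not support that. Site scores of 2 to 4 are AEs; the synopsis plans to summarise AE incidence with no limit to completers, and adds "Maximum intensity and duration of AEs will be summarized by treatment group". AE withdrawals are followed up with a written summary (Section 8), and reasons for discontinuation go into the report to the IRB (Section 11.2). What remains is narrower: leavers' scores below 2 are not made AEs, and no leaver's score of any size would be in the irritation table.

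A third reply is that completers of all nine applications are a reasonable set for cumulative irritation. That also stands, and is why their table should be kept. It does not justify them as the only set, since the objective covers primary or cumulative irritation.

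Finally, no threshold or pass/fail rule is visible, so no stated decision is shown to change.

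**Conclusion.** The point holds conditionally. The synopsis names a completer set for irritation, the protocol foresees exit because of reactions, and no visible text names a wider set. Following the stated rule can therefore remove subjects because of the outcome being measured. The direction is downward if test-material reactors leave Induction more often than others.

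The size is unknown and may be zero. The figures rest on assumed numbers of reactors and exits; a single reaction-related exit with no reacting completers already separates 0/56 from 1/57. The change is worth making because the data already exist, but confidence that an exclusion would occur is only medium while completion remains undefined and Section 6.3 cannot be read.

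A reader might also infer bias in the sensitization result. The documents do not support that: sensitization is read at Challenge, and bias there would need the further assumption that subjects who leave Induction are likelier to react at Challenge.

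**What to change.** State in the synopsis and in Section 7:

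- Irritation is tabulated by site in all subjects with at least one patch and at least one later reading.
- All available Induction scores are used: the maximum score per subject together with the scores by visit or a cumulative score. The maximum alone would not address cumulative irritation.
- Subjects who left, or whose patching stopped early, are flagged with the reason and the site responsible. Leaving should not itself be scored as a reaction, since that would create a composite outcome that the plan does not use.
- The completer table is kept beside this one as supportive and for cumulative irritation over all nine applications.
- Completing Induction is defined, including whether a subject whose patching at a site is interrupted or stopped (Section 8.4) counts as a completer. This must be reconciled with Section 6.3.

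The sensitization analysis needs no change for this point.

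The cost is a wording change and perhaps one CRF field for the site responsible; scores, final evaluations and reasons are already collected. The reported irritation rate may be slightly less favourable. Early leavers for other reasons contribute fewer readings and can dilute the rate. For example, with five reacting completers and four non-reacting early leavers, completers show 5/53 = 9.4% and all patched subjects 5/57 = 8.8%. Showing both tables makes this visible.

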6.1 Design

[figure not shown]
This is a single-center RIPT in healthy male and female subjects aged 18 to 79 years, inclusive. Subjects will be screened for eligibility within 7 days prior to the first dose administration. Subjects will be asked to appear at the Testing Facility on Day 0 for the first application of patches. During the Induction Phase subjects will be patched 9 times in 21 days. Evaluations of the test sites will occur prior to patch application. The scores of these evaluations will be analyzed for irritant contact dermatitis potential.

After an approximately 2 week Rest Phase, subjects will return to the Testing Facility for the Challenge Phase. Virgin sites on the subjects' back will receive patches. The patches will remain on the test sites for two days of continuous skin contact. Evaluations of the sites will occur the day of patch removal and 1 day and 2 days after patch removal. The scores of these evaluations will be analyzed for allergic contact sensitization potential.

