6.3.2 Challenge Phase

6.3.3 Re-Challenge Phase

[figure not shown]
In the event of a significant reaction occurring during the Challenge phase, the PI may decide to schedule a Re-Challenge Patch test for confirmatory purposes. This follow-up investigation will be conducted approximately 2 weeks after the completion of the Challenge Phase. The application of the patch to a virgin test site on the back will be identical to the Challenge Phase. Additionally, the subject may conduct repetitive applications to the anti-cubital fossa for 4 consecutive days. Observations of both test sites will be recorded Days 1, 2 and 3 post application.

Page: 14 of 21

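### The sensitization analysis rests on subjects who complete Challenge, so a positive early Challenge reading followed by withdrawal can fall outside the second primary result

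*Combined protocol and SAP*

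**What the plan says.** Sensitization is one of two primary objectives (synopsis and Section 2): "The second primary objective of this trial is to determine by repetitive epidermal contact, the allergic contact sensitization potential of a test material". The synopsis, under the number of subjects planned and analyzed, sets one population for each objective. For irritation: "Data from all subjects who complete the Induction Phase will be analyzed for irritant contact dermatitis potential". For sensitization, what is to be analyzed is "Data from all subjects who complete the Challenge Phase". The same entry gives the numbers: "Approximately 57 subjects will be enrolled in the trial so that at least 50 subjects will complete the trial".

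Section 6.1 describes three Challenge readings: "Evaluations of the sites will occur the day of patch removal and 1 day and 2 days after patch removal". It says these scores feed the sensitization assessment, but not what happens when a subject has only one or two of them. Section 7 anticipates no statistical methods, and the synopsis promises tabulation of the scores.

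The section on withdrawal of subjects (the second of two numbered 5.4) lists possible reasons for leaving. One is "Experiences a serious or intolerable AE"; another is the subject's own request because of a clinical reaction that the investigator did not think required removal. Sections 6.4.1 and 6.4.2 record any score of 2 to 4 as an adverse event.

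**The concern.** A strong reaction at the patch site is the signal that the second primary objective looks for. Under the withdrawal section it is also a possible reason for the subject to leave. If the analysis set requires completion of Challenge, the outcome can remove the subject from the set in which it is counted.

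The two kinds of result do not need the same data. A qualifying reaction on removal day is a positive finding even if the next two readings never happen. A clear site on removal day is not yet a negative, because a reaction may still appear at the later readings. A completer rule suits the negative but discards the positive. Exclusions caused by reactions all push the result the same way, towards no sensitization.

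In a trial aiming for about 50 completers, the result may turn on a single subject: one omitted reactor is the difference between reporting that none was seen and reporting that one was.

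**Working it through.** **Inputs.** From the synopsis: about 57 enrolled and at least 50 completing. From Section 6.1: three Challenge readings. The numbers of reactors below are assumptions; the documents give no expected reaction rate and no dropout rate.

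**The plan's own figure.** 57 − 50 = 7, and 7/57 = 12.3%. The figure of 57 cannot be derived, since no dropout rate is stated, but it is a plausible allowance: 50/(1 − 0.12) = 56.8, which rounds up to 57. So the plan makes room for about 7 subjects who do not complete. That says nothing about why they leave.

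**How the rule treats each Challenge record.**

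| Challenge record | What it shows | Under the completer rule |
|---|---|---|
| Three readings, one or more positive | Positive | Counted as positive |
| Three readings, none positive | Negative | Counted as negative |
| Positive on removal day or +1 day, then leaves | Positive | Outside the set |
| One or two readings, none positive, then leaves | Undetermined | Outside the set |

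The third row is the problem. Leaving out the fourth row from the negatives is reasonable; leaving out the third loses an observed event.

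**Effect of one or two such subjects.** Exact (Clopper-Pearson) two-sided 95% limits for x reactors in n: the lower limit is the 0.025 quantile of Beta(x, n − x + 1), taken as 0 when x = 0; the upper limit is the 0.975 quantile of Beta(x + 1, n − x).

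- Completers only, 0/50: 0%. The upper limit is 1 − 0.025^(1/50) = 7.1%, so the interval is 0 to 7.1%.
- One excluded reactor restored, 1/51: 2.0% (0.05 to 10.4%).
- Two restored, 2/52: 3.8% (0.5 to 13.2%).

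These denominators add leavers who reacted but none who did not, so they depend on the outcome. Over all 57 enrolled, the figures are 1/57 = 1.8% (0.04 to 9.4%) and 2/57 = 3.5% (0.4 to 12.1%). The choice of denominator moves the rate slightly; the change from zero to one or two reactors remains.

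**How likely is a sensitized subject among 7 non-completers?** If they carried the same assumed sensitization rate p as everyone else, the chance of at least one is 1 − (1 − p)^7:

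- p = 1%: 6.8%
- p = 2%: 13.2%
- p = 5%: 30.2%

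The chance is higher if reactions themselves prompt withdrawal. It covers leaving at any stage; only those who leave after a positive Challenge reading fall in the third row of the table.

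**The case against.** The strongest case against is textual. The synopsis sentence does not say that only completers are analyzed, and completion of Challenge is not defined in the visible text. Section 6.1 and the synopsis entry on statistical methods refer to the scores without a completer limit. This stands as far as it goes: the exclusion is what the sentence means when read as written, not an explicit ban. But it is the only sensitization population in the visible text, and if it is ambiguous, inclusion could be settled after reactions are known.

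Second, the body of Section 6.3, the visit tables and the scoring tables are missing from the available copy. A rule for partial Challenge records could sit there. That cannot be excluded, and its absence from the copy is not a fault of the plan.

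Third, the plan pursues people who react. Section 5.5 has final-visit evaluations done after withdrawal, Section 8 follows anyone withdrawn for an adverse event until the outcome is determined, and Section 6.3.3 allows a repeat test: "In the event of a significant reaction occurring during the Challenge phase, the PI may decide to schedule a Re-Challenge Patch test". From removal day onward only two observation visits remain, so loss at that point may be uncommon. All of this stands, and a reader who inferred that such reactions vanish from the trial's reporting would be wrong. What is missing is any text that carries these data into the sensitization result; Re-Challenge is also optional.

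A reader might also infer that subjects who react during Induction are lost sensitization cases. The documents do not support that. Section 6.1 assigns Induction scores to irritation, an Induction reaction may be irritant rather than allergic, and the withdrawal reasons are only possible ones, so a reaction need not lead to withdrawal or a missed Challenge. Nor do the documents state any labelling use of the result, so the point cannot rest on one.

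**Conclusion.** The point holds in a limited form and should be fixed; it is not a fatal flaw. As written, the completer rule can leave an observed positive Challenge reading out of the second primary result, and the resulting bias runs towards no sensitization. In the illustration, one such subject moves the result from 0/50 (upper 95% limit 7.1%) to 1/51 = 2.0% (upper limit 10.4%).

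This rests on three assumptions: that the synopsis sentence defines the set, that no handling rule exists in the unseen part of Section 6.3, and that at least one subject reacts early in Challenge and then leaves. The documents give no means of estimating how often the last would happen. Subjects who stop before Challenge with a test-site reaction are an unresolved group to be shown, not presumed positives.

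**What to change.** In the synopsis and Section 7, state that:

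1. The sensitization set is every subject who receives the Challenge patch and has at least one Challenge reading, including the one on removal day.
2. A qualifying reaction at any Challenge reading counts as positive, whether or not later readings exist. What qualifies should be tied to the plan's own scoring scale.
3. A negative requires all three readings. Subjects with incomplete readings and no positive are reported separately as unevaluable, with their number.
4. Subjects who stopped before Challenge with a reaction at the test-material site are listed separately as unresolved, and one sensitivity line counts them as reactors.

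If Section 6.3 already contains a rule for partial Challenge records, make the synopsis agree with it.

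The cost is a few sentences and one or two table rows, with no new visits or data. The downside for the sponsor is that the reported rate may be slightly less favourable. The rule should be in place before any Challenge scores are known.
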